5.4.2.4 AE of Special Interest

Please refer to the placebo-controlled period SAP for AEs of special interest. The same tables as described in placebo-controlled period SAP will be summarized for LTE by LTE treatment groups.

	Statistical Analysis Plan Long-Term Extension Period	V1.0
---	--	-------------

5.4.3 Clinical Laboratory Data

The following clinical laboratory parameters are assessed in the protocol:

- Hematology: red blood cell count, platelet count, hemoglobin level, hematocrit, mean corpuscular volume, mean corpuscular hemoglobin, mean corpuscular hemoglobin concentration, and total white blood cell count with absolute counts and percentages of neutrophils, monocytes, lymphocytes, eosinophils, and basophils
- Blood chemistry: total protein, albumin, creatinine, BUN, uric acid, bilirubin (total and direct), alkaline phosphatase, ALT, AST, lactate dehydrogenase, gamma-glutamyl transferase, glucose, calcium, phosphorus, bicarbonate, chloride, sodium, and potassium
- Urinalysis: color, specific gravity, pH, protein, glucose, leukocyte esterase, blood, and ketones (and microscopic examination, if abnormal)
- Coagulation: Activated Partial Thromboplastin Time (APTT), Prothrombin Intl. Normalized Ratio (INR), Prothrombin Time (PT)

Analysis period will be specified for each table or figure. Unless otherwise specified, all the laboratory tables will be summarized by LTE treatment group. Listings will include all data in the study, with an indicator of the study period (pre-dosing, placebo-controlled, or LTE) for each record when the assessment occurred. Listings will be presented by PC treatment group.

Study day and analysis visit window for analyses using LTE baseline will be derived based on the first day of study drug in LTE. Details are specified in [Appendix I](#).

5.4.3.1 Quantitative analyses

For numeric laboratory parameters, actual values will be summarized by visit for all the visits in the placebo-controlled and LTE active treatment period. Number of evaluable subjects, mean, standard deviation, 25% and 75% quartiles, min and max values will be presented at each visit. Plots of mean actual values (with standard error) at each visit for all the visits in the placebo-controlled and LTE active treatment period will be provided.

Summary of change from baseline and percent change from baseline for numeric laboratory parameters will be done on the placebo-controlled and LTE active treatment period. LTE baseline will be used for late start high-dose group subjects, while placebo-controlled baseline will be used for the rest of the subjects (low-dose BIIB092 125mg/4weeks, low-dose BIIB092 375mg/12weeks, medium-dose, early start high-dose). Number of evaluable subjects, mean, standard deviation, 25% and 75% quartiles, min and max values will be presented at each visit.

Listings of individual laboratory measurements by patients for all the parameters will be provided.

Visit windows for by visit summaries

CONFIDENTIAL

The information contained herein may not be used, disclosed, or published without the written consent of Biogen MA Inc.

	Statistical Analysis Plan Long-Term Extension Period	V1.0
---	---	-------------

For Laboratory data that are summarized by visit, assessment from all scheduled visits, EOT visit, EOS visit and unscheduled visits will be mapped to an appropriate analysis visit using a windowing scheme ([Appendix I](#)).

5.4.3.2 Qualitative analyses

For qualitative analyses, all values will be included (not just the “analyzed record” within each visit window in the quantitative analyses).

Shift analyses

Laboratory data will be summarized using shift tables where appropriate for the placebo-controlled and LTE active treatment period. Each subject’s hematology, blood chemistry and urinalysis values will be flagged as “low”, “normal”, or “high” relative to the normal ranges of the central laboratory or as “unknown” if no result is available.

For each parameter, the analysis will be based on subjects with at least one post-baseline value. Shifts from baseline to high/low status will be presented for hematology, blood chemistry coagulation, serology, and urinalysis. Shift to low includes normal to low, high to low, and unknown to low; Shift to high includes normal to high, low to high, and unknown to high. Subjects need to have at least one post-baseline evaluation and a baseline value not low or high (including missing) in order to be included in the analysis for corresponding categories in the analyses.

For early start subjects, the placebo-controlled baseline will be used and shifts that occurred in either placebo-controlled or LTE period will be included. For late start subjects, the LTE baseline will be used and shifts that occurred in the LTE period based on LTE baseline will be included.

Potentially Clinically Significant laboratory abnormalities analyses

Please refer to the placebo-controlled SAP for the parameters and criteria for potentially clinically significant laboratory abnormalities analyses.

The number of subjects with potentially clinically significant laboratory abnormalities post-baseline will be summarized for the placebo-controlled and LTE active treatment period.

Subjects need to have at least one post-baseline evaluation in the active treatment period and a baseline value not potentially clinically significant (including missing) in order to be included in the analysis.

Same as the shift analysis, for early start subjects, the placebo-controlled baseline will be used and abnormalities that occurred in either placebo-controlled or LTE period will be included. For late start subjects, the LTE baseline will be used and PCS abnormalities that occurred in the LTE period based on LTE baseline will be included.

CONFIDENTIAL

The information contained herein may not be used, disclosed, or published without the written consent of Biogen MA Inc.

	Statistical Analysis Plan Long-Term Extension Period	V1.0
---	---	-------------

Potential serious hepatotoxicity

In this SAP, we define potential serious hepatotoxicity as ALT or AST > 3x ULN and total bilirubin > 2x ULN at any time post-baseline in the placebo-controlled and LTE active treatment period (not necessarily concurrent). A scatterplot of the maximum post-baseline ALT or AST value relative to ULN and maximum post-baseline total bilirubin value relative to ULN (not necessarily concurrent) for each subject will be provided. A line plot of ALT, AST, ALP and total bilirubin values over time in the active treatment period for subjects with potential serious hepatotoxicity will be provided. In addition, subjects with ALT > 1x ULN, >3x ULN, >5x ULN, >10x ULN or >20x ULN, subjects with AST > 1x ULN, >3x ULN, >5x ULN, >10x ULN or >20x ULN, subjects with total bilirubin >1x ULN or >2x ULN, subjects with ALP >1x ULN or >1.5x ULN, and subjects with AST or ALT > 3x ULN post-baseline accompanied by concurrently elevated total bilirubin >1.5x ULN or > 2x ULN in the active treatment period will be presented. A listing of subjects with potential serious hepatotoxicity will be provided with the concurrent records labeled. Concurrent is defined as on the same day.

5.4.4 C-SSRS Data

Suicidal ideation events include 11 categories: (1) Wish To Be Dead, (2) Non-Specific Active Thoughts, (3) Active Thoughts Without Intent To Act, (4) Active Thoughts With Some Intent—No Plan, (5) Active Thoughts with Plan and Intent. Suicidal behavior events include: (6) Preparatory acts or behavior, (7) Aborted Attempt, (8) Interrupted Attempt, (9) Actual Attempt, (10) Suicidal behavior, (11) Completed Suicide. Another “Yes/No” question of whether the subject has engaged in non-suicidal self-injurious behavior is also collected.

The analysis will be based on the safety population. Number of subjects in each ideation category at any post-baseline visit, number of subjects in each suicidal behavior category at any post-baseline visit, number of subjects with at least one suicidal ideation or behavior event at any post-baseline visit, and subjects who have engaged in non-suicidal self-injurious behavior at any post-baseline visit will be summarized in the placebo-controlled and LTE active treatment period. A listing of C-SSRS data by subjects will be provided.

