 - Anticonvulsants that have significant effects on cognition per the Investigator's opinion and/or anticonvulsants used for treatment of seizures. Anticonvulsants with limited cognitive effects, such as lamotrigine, pregabalin, levetiracetam for treatment of pain, and other non-epilepsy indications are allowed if, in the opinion of the Investigator, they are not producing sedation or contributing to cognitive impairment. The participant must have been on a stable dose for 8 weeks prior to Screening Visit 1 and during the Screening Period up to Study Day 1.
 - Antidepressants that may, in the Investigator's opinion, affect the participant's cognition (e.g., tricyclic antidepressants). Mild depression or depressive mood arising in the context of AD are not criteria for exclusion. Use of antidepressants is allowed if at stable doses for 8 weeks prior to Screening Visit 1 and during the Screening Period up to Study Day 1.
 - High-dose antipsychotics used on a regular basis. Low doses of atypical and typical antipsychotics if used on an as-needed basis or if used at a stable dose for 8 weeks prior to Screening Visit 1 and during the Screening Period up to Study Day 1. The definition of "low dose" and "high dose" should be judged by the Investigator, and the Medical Monitor can be consulted if needed.
 - Anticholinergics such as benztropine. Anticholinergics for bladder control with limited cognitive effects are permitted but should be avoided if possible.
 - Prior use of levodopa or anti-Parkinsonian medications including dopaminergic agents, amantadine, selegiline, benztropine, and monoamine oxidase (MAO) inhibitors prescribed for the treatment of Parkinsonism or Parkinson's disease.

CONFIDENTIAL

The information contained herein may not be used, disclosed, or published without the written consent of Biogen MA Inc.

- Use of prescription narcotic medications within 4 weeks prior to Screening Visit 1. After randomization, short-term use of prescription narcotics is allowed for specific situations (e.g., after surgical procedures) and if administered at least 24 hours prior to cognitive testing.
- Use of any drug of abuse, including but not limited to, amphetamine, cannabis, cocaine, opiate, propoxyphene, methadone, methaqualone, phencyclidine, or barbiturates.

When necessary, the Medical Monitor should be contacted with any questions.

- 31. Vaccinations within 10 days prior to randomization (Study Day 1).

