3.1 Analysis Sets

- **Full Analysis Set (FAS):**
The FAS includes all randomized subjects who received at least one dose of study treatment (BIIB092 or placebo). In analyses performed on the FAS, subjects will be analyzed, based on the intention-to-treat principle, according to their randomized treatment assignment regardless of treatment received.
- **Safety Analysis Set:**
The safety Analysis Set includes all randomized subjects who received at least one dose of study treatment (BIIB092 or placebo), essentially the same set of participants included in the FAS. In analyses performed on the Safety Analysis Set, subjects will be analyzed according to their actual treatment received.
- **Safety MRI Evaluable Set:**
The Safety MRI Evaluable Set is defined as subjects in the FAS who had at least one post-baseline safety MRI scan.
- **Serum PK Evaluable Set:**
The serum PK evaluable set is defined as subjects in the FAS who had at least one measurable post-baseline BIIB092 concentration in serum before the End of Study of LTE.
- **CSF PK Evaluable Set:**
The CSF PK evaluable set is defined as subjects in the FAS who had at least one measurable post-baseline BIIB092 concentration in CSF.
- **CSF PD Evaluable Set:**
The CSF PD evaluable set is defined as subjects in the FAS who had lumbar puncture (LP), which will be used in analyses, such as subject accounting and summary of AE related to LP. The CSF PD Modified Evaluable Set is defined as subjects in the FAS who have baseline and at least one post baseline assessment of the specific parameter being analyzed in CSF.
- **Tau PET Evaluable Set**
The tau PET evaluable set is defined as subjects in the FAS who had tau PET, which will be used in analyses, such as subject accounting and summary of AE related to tau PET. The tau PET Modified Evaluable Set is defined as subjects in the FAS who had a valid baseline and a post-baseline tau PET SUVR measure using the 18F-MK6240 tracer.

	Statistical Analysis Plan Long-Term Extension Period	V1.0
---	---	-------------

- Anti-drug antibody (ADA) Evaluable Set:
The evaluable set for anti-drug antibody is defined as subjects in the FAS who have an evaluable post-baseline ADA sample.

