5.1 General Considerations

Summary tables will be presented using descriptive summary statistics. For continuous variables, summary statistics will generally include: number of subjects with data, mean, standard deviation, median, 25% percentile, 75% percentile, minimum and maximum. For categorical variables, this will generally include: number of subjects randomized or dosed, number with data, and the percent of those with data in each category.

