Week 116	813	[772, 953]	Week 196
Week 156	1093	[954, 1163]	Week 224
Week 176	1233	>1163	Week 238

Day 1 is the first infusion day in LTE period

Table 12. Visit Windows for tau PET data

Analysis visit *	Target visit day	Analysis visit window
Baseline	1	Most recent non-missing pre-dose value
Week 52	364	[120, 456]
Week 78	547	[457, 727*]
Week 152	1065	[728, 1324]
Week 226	1583	>1325

* 180 days after Week 78 target date.

CONFIDENTIAL

The information contained herein may not be used, disclosed, or published without the written consent of Biogen MA Inc.

Table 13. Visit Windows for C-SSRS data using Placebo controlled baseline

Analysis visit	Target visit day	Analysis visit window
Baseline	1	Most recent non-missing pre-dose value
Week 24	169	[2, 267]
Week 52	365	[268, 456]
Week 78	547	[457, the last day of the PC period ¹]
Week 104	729	[the start day of the LTE period ² , 813]
Week 128	897	[814, 981]
Week 152	1065	[982, 1149]
Week 176	1233	[1150, 1317]
Week 200	1401	[1318, 1492]
Week 226	1583	>1492

1. The end day of the placebo-controlled period is the last day before the first infusion in LTE, and is the last day in study for subjects who do not enter LTE.
 2. The start day of the LTE period is the day of first infusion in LTE period.

Table 14. Visit Windows for C-SSRS by Visit Summaries using LTE Baseline

Analysis visit	Target visit day	Analysis visit window	Protocol visit
Baseline	Most recent non-missing value prior to the first infusion in LTE	Most recent non-missing value prior to the first infusion in LTE	Week 78
Week 24	169	[the start day of the LTE period, 253]	Week 104
Week 52	337	[254, 421]	Week 128
Week 78	505	[422, 589]	Week 152
Week 104	673	[590, 757]	Week 176
Week 128	841	[758, 932]	Week 200
Week 152	1023	> 932	Week 226

Day 1 is the first infusion day in LTE period

Table 15. Visit Windows for safety MRI data with placebo-controlled baseline

Analysis visit	Target visit day	Analysis visit window
Baseline	1	Most recent non-missing pre-dose value
Week 28	197	[90, 281]
Week 52	365	[282, 456]
Week 78	547	[457, the last day of the PC period ¹]
Week 104	729	[the start day of LTE period ² , 911]
Week 156	1093	[912, 1338]
Week 226	1583	≥ 1339

1. The end day of the placebo-controlled period is the last day before the first infusion in LTE, and is the last day in study for subjects who do not enter LTE.
 2. The start day of the LTE period is the day of first infusion in LTE period.

Table 16. Visit Windows for safety MRI data with LTE baseline

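### The C-SSRS table in SAP 5.4.4 makes no comparison with baseline, so suicidality carried over from before BIIB092 cannot be told apart from new or worsened suicidality

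*SAP*

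**What the plan says.** SAP Section 5.4.4 lists five ideation and six behaviour categories. For the combined placebo-controlled and LTE active treatment period it plans the "Number of subjects in each ideation category at any post-baseline visit", the same count for each behaviour category, the "number of subjects with at least one suicidal ideation or behavior event at any post-baseline visit", and a count for self-injury without suicidal intent. It adds a by-subject listing. On population it says "The analysis will be based on the safety population". It plans no shift table and no row for new or worsened status, and it states no percentage or denominator. It does not refer to the placebo-controlled SAP, which was not available for this review.

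Section 3.2 defines the active treatment period. Early starters contribute all their data; late starters, who took placebo first, contribute only LTE data. Section 3.4 defines an active-treatment baseline as the last value before the first BIIB092 dose. Appendix I gives C-SSRS windows for both baselines in Table 13 and in "Table 14. Visit Windows for C-SSRS by Visit Summaries using LTE Baseline".

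The Protocol (Section 16.3.2.6) asks only for descriptive C-SSRS summaries by dose group and for all active treatment combined.

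**The concern.** A suicidality table in a safety report is read for one purpose: whether ideation or behaviour appeared or got worse after the drug was started. A count of any post-baseline report does not answer that. A participant whose ideation predates BIIB092 and who reports the same thing again is entered exactly like one who reports it for the first time. For late starters, ideation that arose on placebo and persists appears under 2000 mg.

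Other safety analyses in the SAP treat this as something to handle. For potentially clinically significant laboratory values it says "Subjects need to have at least one post-baseline evaluation in the active treatment period and a baseline value not potentially clinically significant", with missing baselines kept in. Safety is the primary objective of the LTE, and the C-SSRS is the only scheduled instrument for this risk, so a table that mixes carried-over and emergent events loses the information it is there to give.

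**Working it through.** The plan gives no C-SSRS rate, so there is no figure to reproduce. The check is a comparison of texts, followed by an illustration on assumed inputs.

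**1. How the SAP's safety analyses treat baseline**

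| Analysis | Condition on baseline |
|---|---|
| Adverse events, 5.4.2 | Must start or worsen after the first LTE infusion |
| Laboratory shifts and PCS values, 5.4.3.2 | Post-baseline value required; baseline free of the finding or missing; placebo-controlled baseline for early start, LTE baseline for late start |
| Potential serious hepatotoxicity, 5.4.3.2 | None |
| ECG shift, 5.4.5.1 | Baseline normal or unknown |
| Safety MRI, 5.4.9 | New or worsening edema; new microhemorrhage and siderosis; the macrohemorrhage row does not say new |
| C-SSRS, 5.4.4 | None |

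**2. Whether the data exist**

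Protocol Tables 1 to 4 schedule the C-SSRS at screening, at Weeks 24, 52 and 78, and in the LTE at Weeks 104, 128, 152, 176, 200 and 226. Both baselines are collected, defined and windowed, but 5.4.4 plans no output that uses them.

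**3. A worked case**

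Late starter A reports category 1 ideation at Week 78 (on placebo) and category 1 again at Week 104. Late starter B reports nothing at Week 78 and category 1 at Week 104. Both add one to the category 1 row of the late-start column. Under the laboratory PCS rule, A would be left out and B counted.

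**4. Illustration of size (all inputs assumed)**

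Let b be the share with ideation at baseline, q the share of those who report it again at no higher category, and r the share with new ideation among those without it at baseline.

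- Planned share = (1 − b)r + bq
- Carried-over part of those counted = bq / [(1 − b)r + bq]

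With r = 5% and q = 50%:

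| b | Planned share | Carried-over part |
|---|---|---|
| 2% | 0.98 × 5% + 0.02 × 50% = 5.9% | 1.0 / 5.9 = 17% |
| 5% | 0.95 × 5% + 0.05 × 50% = 7.25% | 2.5 / 7.25 = 34% |
| 10% | 0.90 × 5% + 0.10 × 50% = 9.5% | 5.0 / 9.5 = 53% |

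Among participants without baseline ideation the figure is 5.0% throughout. With q from 25% to 100%, the planned share runs from 5.4% (b = 2%, q = 25%) to 14.5% (b = 10%, q = 100%). Participants who return at a higher category belong in a worsened row, so the gap narrows to the extent that this happens.

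The groups are small. If over-enrolment was proportional, a low-dose regimen group is about 44 × 654/528 = 54.5 people, and one person is 1/54.5 = 1.8 percentage points.

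**5. Denominator**

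Section 5.1 says categorical summaries will generally show the "number of subjects randomized or dosed, number with data, and the percent of those with data in each category". Section 5.4.1.3 defines a safety incidence proportion over everyone in the analysis population. Section 5.4.4 does not say which applies. If u is the share with no on-drug C-SSRS, the first rule leaves r unchanged and the second gives r(1 − u). With r = 5%, that is 4.75%, 4.5% or 4.0% for u = 5%, 10% or 20% (assumed values).

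**The case against.** **The counts are correct for their label, and nothing is hidden.** A row headed any post-baseline occurrence reports just that. It errs towards inclusion, and the hepatotoxicity analysis in the same SAP uses the same convention. The display is descriptive, with no test. This stands as far as it goes: the rows are not wrong. They leave out the comparison a reader needs.

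**The listing solves it.** A by-subject listing is planned, and by default (Section 5.2) listings cover all study data with a period indicator. A reader can trace carried-over ideation, but has to rebuild by hand the table the report should contain.

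**Baseline ideation may be rare.** The Protocol says "Mild depression or depressive mood arising in the context of AD are not criteria for exclusion". Exclusions 7, 9 and 24, however, cover unstable psychiatric illness, long-term major depression or bipolar disorder with a recent active episode, and other clinically significant psychiatric disease, and LTE exclusion 1 covers psychiatric contraindications. Several criteria are redacted, so it cannot be said that no criterion addresses ideation. This stands, and it is why no prevalence can be claimed.

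**Unassessed participants counted as event-free.** A reader might infer this from the naming of the safety population. The documents do not support it: that phrase sets who is eligible, 5.4.4 promises counts only, and the general rule in 5.1 would leave out those without data. Nor is there a basis for assuming many are missed. Participants who stop treatment are asked to keep attending, the C-SSRS is scheduled at the early termination visit, and the waiver in Protocol Section 10.3 covers only efficacy assessments, whereas Section 14.1 lists the C-SSRS as a safety assessment. What remains is an unresolved choice between two rules.

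**Conclusion.** The point holds for the baseline comparison. As written, the table cannot separate suicidality carried over from before BIIB092 from suicidality that is new or worse. This departs from how the SAP handles most other safety findings. Carried-over ideation or behaviour enters only if it is reported again after the first BIIB092 dose.

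The denominator point is one of clarity: two general rules conflict and 5.4.4 does not choose between them.

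The size is unknown. The 5.9% to 9.5% range rests on assumed values of b, q and r, none of which comes from the documents.

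A reader might go further and infer bias between early and late start, since their baselines fall at different times and a late starter's first scheduled on-drug C-SSRS is at Week 104, 24 weeks after the first dose at Week 80. That is possible but not shown: the documents give neither baseline ideation nor assessment completeness by group.

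The placebo-controlled SAP may hold further C-SSRS rules, but 5.4.4 does not call on them.

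**What to change.** In SAP Section 5.4.4:

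- Add rows for participants with new or worsened ideation, new or worsened behaviour, and either. Compare the worst post-baseline category with the active-treatment baseline: placebo-controlled baseline for early start, LTE baseline for late start.
- Keep participants with a missing baseline in these rows, as Section 5.4.3.2 does, so that no event is lost.
- State the ranking used. The numbered behaviour list includes a general suicidal behaviour item (10) that does not read as a grade of severity.
- State the recall period of the baseline assessment, which the documents do not give. Because baseline is the last value before first BIIB092, ideation reported earlier on placebo but absent at Week 78 would count as emergent; a footnote can say so.
- State that any C-SSRS percentage uses participants with at least one C-SSRS after first BIIB092, and show that number.
- Keep the planned any-post-baseline counts as supportive rows.

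The cost is a few lines of SAP text and one more block in an existing table. No new data are needed.
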